Specific Aim 2: Manual function. To evaluate the effects of the training program incorporating ride-on-toys on manual abilities and spontaneous use of the affected arm in children with hemiplegic CP as measured using standardized tests and objective/kinematic measures.

- Aim 2A: We hypothesize that there will be greater improvements in affected arm active movement control and spontaneous functional use as assessed using standardized tests (Quality of Upper Extremity Skills and Shriner's Hospital Upper Extremity Evaluation) and a parent-rated questionnaire (ABILIHAND-Kids), following the intervention phase compared to the control phase. During the intervention phase, children will also show improvements in movement control and maneuverability of the ride-on-toy from an early to a late training session.
- Aim 2B: We hypothesize that children will also show improved motor control and movement kinematics during reaching in terms of increased movement speed, smoothness, straightness, and symmetry, decreased movement variability, and improvements in peak and average velocity of reaching. Children will also show greater improvements in daily arm activity measured through objective wrist-worn activity monitors during the intervention compared to the control phase.

Clinical Impact: This project, led by an early career investigator, strategically leverages the expertise of an interdisciplinary team that comprises experts from physical therapy, occupational therapy, and biomedical engineering who are well suited to implement the proposed project. Our work aligns with the strategic plan of the AACPDM in (1) embracing innovative approaches to advance knowledge and practice in the field of CP and (2) fostering research that will generate new knowledge and evidence to inform care of people with CP. The proposed research will provide evidence to support an innovative, child-friendly, low-cost, home-based training program using commercially-available ride-on-toys that can be implemented by clinicians and families to promote spontaneous, self-initiated practice using the affected UE and improved manual function in children with hemiplegic CP.

RESEARCH METHODS/PLANS

1. Study design: Single group longitudinal design. Children will be observed for a 6-week control phase (conventional treatment-as-usual) followed by a 6-week experimental phase (conventional therapy + RNT).

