1. Primary: Adherence – The toy will collect data on amount of use during training. Researchers and caregivers will also maintain logs during the intervention phase to document training duration and child engagement. 2. Primary: Treatment satisfaction and engagement - Children will complete the valid and reliable, 16-item Physical Activity Enjoyment Scale (PAES) to rate their experience.⁶⁷⁻⁶⁹ Training sessions (one early, mid, and late session each) will be video-coded for child affect (i.e., smile rates, % duration of positive/interested and negative affect) and attention (i.e., % duration of attention to task-relevant targets). Children and/or caregivers will fill out exit questionnaires to assess training satisfaction, enjoyment, repeatability, and caregiver burden. 3. Primary: Treatment fidelity – An unbiased coder will randomly code video data (one each of early, mid, and late sessions) from researcher-delivered sessions using fidelity checklists to assess adherence to the training protocol. Trainers will also fill out posttest exit questionnaires to assess ease of implementation of RNT. 4.2.1. Aim 2A: Manual abilities and spontaneous affected UE use will be assessed as follows -1. Primary: Quality of Upper Extremity Skills Test (QUEST)⁷⁰– This criterion-referenced reliable and valid test assesses UE movement quality using unimanual items scored on a dichotomous scale in 4 domains: grasp, dissociated movement, protective extension, and weight bearing. The scale is valid up to 12 years of age.⁷¹ 2. Primary: Shriner's Hospital Upper Extremity Evaluation (SHUEE)⁷²– This video-based valid and reliable test assesses affected UE use spontaneously and on tester demand in 16 bimanual tasks in 3-18-vear-old children. It has 3 parts: spontaneous functional analysis, dynamic positional analysis, and grasp-release analysis. 5. Secondary: Navigation control and accuracy – Early & late training sessions will be coded for (1) % duration of assisted (child needs trainer-provided manual assistance) versus independent navigation, (2) average duration and number/session of child-initiated, movement bouts normalized by driving time (a bout comprises 1 acceleration and 1 deceleration phase), and (3) rates/session of path deviations and obstacle bumps. 4. Secondary: ABILHAND-Kids⁷³– This valid and reliable parent-rated questionnaire rates the child's difficulty level (3-point ordinal scale of 'impossible', 'difficult', or 'easy') in performing 21 bimanual skills independently. 4.2.2. Aim 2B: 1. Primary: Kinematic measures – Data will be collected during a unilateral and bilateral reachgrasp task at self-selected speed involving different objects (foam ball, rattle, and square block) placed at half arm's length (near) and at arm's length (far) on the table. Sensors (Inertial Measurement Units (IMUs)) will be placed on both hands, both forearms, both arms, and the C7 spinous process. We will assess the speed. smoothness, variability, and symmetry of reaching trajectories. Kinematic and motion data will also be obtained during weekly researcher-delivered training sessions and through toy-mounted sensors. 2. Secondary: Arm activity – Wrist-worn Actigraph activity monitors will be worn during first and last week of

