
control and intervention phases to assess changes in daily arm activity over the course of the study. **5. Training protocol** – Children will continue to receive conventional therapy such as physical and occupational therapy throughout the study. During the first 6-week control phase, researchers will keep track of conventional therapy received (frequency, duration/session, type) on a weekly basis through parent interviews/training logs. In the second 6-week intervention period, in addition to conventional therapy, children will receive ride-on-toy navigation training (RNT). Researchers will provide 2 sessions/week and caregivers will provide 2 sessions/week each lasting 20-30 minutes. Training will occur at the child's home/school/community spaces like YMCA, playground, etc. Families without access to such spaces will have the option to visit the PI's lab for training. The toy can be driven on different surfaces, e.g., wood, grass, concrete, carpet, etc., allowing for flexibility in accommodating unique space-related constraints faced by families. During weekly visits, researchers will coach caregivers for caregiver-provided sessions. Trainer will fill out training diaries to log details of intervention delivery and child progress. Children will use only their affected arm to move the joystick and the unaffected arm will be enclosed in a soft restraint to encourage use of the affected side during RNT. Each session will include periods of "free play" (child can navigate freely through their physical environment using toy) and "structured play" (child will participate in multi-directional navigation games such as shape mazes, treasure hunts, and obstacle courses). The intervention is based on the motor learning- and familycentric practice-based training principles: variable and repetitive practice, progressive challenges tailored to child needs, activities promoting problem-solving and trial-and-error learning, immediate visual and auditory feedback, playful exploration, incorporation of child-preferred toys/themes into games to increase motivation, and involvement of caregivers and siblings during training. Training will emphasize active UE control of the joystick for starting and stopping the toy, moving steadily forward and backward, turning to the right and left, 180° and 360° turns on both sides, and avoiding obstacles. Activities will also involve small toys/props to encourage gross and fine motor movement and control of affected UE. Trainers will follow a least-to-most prompting hierarchy involving gestural, verbal, and finally hand-on-hand assistance per the child's needs during training. **6.** Project timeline – Please see detailed study timeline below.

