
Proposed study activities	Year 1	Year 2			
(Q indicates Quarter)	Oct - Dec	Jan-Mar	Apr-Jun	Jul-Sep	Oct-Dec
Intervention development and IRB Approval					
Ride-on-toy modifications and retrofitting					
Recruitment					
Testing/training: Round 1 (5 children)					
Testing/training: Round 2 (5 children)					
Testing/training: Round 3 (5 children)					
Data analysis					
Data dissemination & preparation for R21/R34 grant					

7. Dependent variables and Statistical analyses - For all coded video data, 2 independent coders will rate 20% of the data to establish inter- and intra-rater reliability of over 90%. Standardized tests will be compared between control and intervention phases, training-specific measures will be compared between early, mid, and late training sessions. All kinematic and activity data will be post-processed using custom MATLAB programs. Dependent variables from pretest-mid-point-posttest measures include: (a) total unilateral scores from affected and unaffected sides on sub-tests of the QUEST, (b) total and % scores on sub-sections on the SHUEE, (c) bilateral range of motion, maximum joint angles, peak and average velocity, total movement time, number of movement units, movement straightness, movement variability, and smoothness (e.g. jerk, dimensionless jerk, and log dimensionless jerk)^{74,75} during kinematic tasks, and (d) raw scores on the ABILHAND-Kids and PAES questionnaires. Dependent variables for training-specific measures include: (a) rates of smiles and % duration of positive/interested versus negative affect. (b) % duration of assisted and independent mobility. (c) number and duration of movement bouts during navigation using the ride-on-toy, (d) outcomes derived from kinematic data (as listed in point (c) above) during the training-specific navigation test, and (e) activity counts collected from activity monitors. All data will be evaluated for assumptions of parametric statistics and general or generalized models will be selected accordingly. Variables that violate distributional assumptions of normality will be analyzed using generalized linear model (GLM) procedures, which enable the use of non-Gaussian error models. We anticipate limited missing data because attrition rates are typically low in home-based versus clinic-based programs.^{76,77} When applicable, missing data will be evaluated to determine if it is completely at random. If random, multiple imputation by maximum likelihood estimation will be used.⁷⁸

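### Section 7 assigns wrist-monitor activity counts to a comparison within training, which cannot test the Aim 2B hypothesis of intervention against control phase

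*Combined protocol and SAP*

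**What the plan says.** Specific Aim 2, Aim 2B, states the arm-activity hypothesis as a comparison of phases: "greater improvements in daily arm activity measured through objective wrist-worn activity monitors during the intervention compared to the control phase".

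Section 4.2.2 makes arm activity a secondary measure. The monitors are put on in the opening and closing week of both "control and intervention phases to assess changes in daily arm activity over the course of the study". That gives four wear weeks per child, two in each phase.

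Section 5 gives ride-on-toy navigation training (RNT) only in the second six-week period.

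Section 7 states two comparisons. The first is "Standardized tests will be compared between control and intervention phases". The second is "training-specific measures will be compared between early, mid, and late training sessions". It then sorts the dependent variables into two lists. The list introduced by "Dependent variables from pretest-mid-point-posttest measures include" spans both phases and does not contain activity counts. The training-specific list does, as its last item: "e) activity counts collected from activity monitors".

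**The concern.** Section 7 is where the analyses are specified, and it puts this outcome under a comparison that does not match its hypothesis. Early, mid and late training sessions all lie in the intervention phase, so the two control-phase wear weeks have no role in the stated analysis.

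The design has a single group, so each child's change over the control phase is the only comparator within the trial. If it is left out, growth, season, habituation to the monitor or the continuing conventional therapy could each produce a rise that looks like an RNT effect. An analyst who followed section 7 would report an uncontrolled change and leave the Aim 2B arm-activity hypothesis untested.

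**Working it through.** **Step 1: trace the outcome through the document.**

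| Place | What it fixes for arm activity |
|---|---|
| Aim 2B | Improvement in the intervention phase against improvement in the control phase |
| Section 4.2.2 | Four wear weeks: control first and last (C1, C2), intervention first and last (I1, I2) |
| Section 5 | Training sessions in the intervention phase only |
| Section 7 | Early, mid and late training sessions compared |

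Aim 2B corresponds to (I2 − I1) − (C2 − C1). The section 7 comparison has three occasions. At most two of them (I1, I2) have a wear week, the mid one has none, and C1 and C2 do not enter. The Aim 2B contrast cannot be estimated from it. The one design layout the plan names, the 1 x 3 layout with three time points in section 8, does not fit four wear weeks either.

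**Step 2: check the calculation method.** The plan gives no SD, trend or effect for activity counts. Its only design figure is in section 8: 82% power with 15 children, effect size 0.80 and two-sided alpha 0.05. A noncentral-t calculation for a paired t test gives 82.1%. The same calculation is used below.

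**Step 3: variances.** Let s be the within-child SD of one week's count, with independent weekly errors (assumed).
- Within-phase change, I2 − I1: variance 2s²; standard error √(2/15) s = 0.365 s.
- Between-phase contrast, (I2 − I1) − (C2 − C1): variance 4s²; standard error √(4/15) s = 0.516 s.
- Alternative contrast, (I2 − C2) − (C2 − C1) = I2 − 2C2 + C1: variance (1 + 4 + 1)s² = 6s²; standard error √(6/15) s = 0.632 s.

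The standard error of the second is √(4/2) = 1.41 times that of the first.

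**Step 4: false-positive rates with no RNT effect.** The shift d is assumed, in units of s. The standardised effect is d/√2 for the within-phase test and d/2 for the between-phase contrast.

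| Shift d | Equal trend in both phases: within-phase test | Equal trend: between-phase contrast | Shift in control phase only: between-phase contrast | Control only: within-phase test |
|---|---|---|---|---|
| 0.25 | 9.8% | 5% | 7.4% | 5% |
| 0.5 | 24.8% | 5% | 14.7% | 5% |
| 1.0 | 72.2% | 5% | 43.8% | 5% |

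A simulation of 40,000 trials agreed: 9.8%, 24.8% and 72.4% for the within-phase test and 4.9–5.0% for the between-phase contrast under equal trends; 7.6%, 14.8% and 43.5% for the between-phase contrast under a control-only shift.

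**Step 5: power.** At n = 15, two-sided 0.05 and 80% power, the detectable standardised difference is 0.778.
- Within-phase change: 0.778 × √2 = 1.10 s.
- Between-phase contrast: 0.778 × 2 = 1.56 s.
- Alternative contrast: 0.778 × √6 = 1.91 s.
- A true difference of 1.10 s gives the between-phase contrast a standardised effect of 1.10/2 = 0.550 and 51% power.
- I1 is already a treated week. If a fraction 0, 0.25 or 0.5 of a 1.56 s effect is present by then, the between-phase contrast has 80%, 56% or 29% power. The alternative contrast has 63% in each case.

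**The case against.** The strongest reply is that the intended comparison is clear from the rest of the document. Aim 2B names both phases, and section 4.2.2 schedules wear in both and gives change over the whole study as the purpose. The section 7 sentence is also loose for other items: section 4.2.1 has navigation control coded in early and late sessions only, with no mid session. The phase comparison names only standardized tests, so a strict reading would leave the reaching kinematics without one as well. Both lists are introduced as inclusive rather than exhaustive, and weekly monitor data fit neither heading well. On this view the fault is a drafting slip in a secondary outcome of a 15-child pilot.

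Much of this stands. It may well be a slip, the control weeks do have a stated purpose in section 4.2.2, and the rejection rates rest on assumed trends and on a two-week paired test that the plan does not itself specify. The 5% for the between-phase contrast follows directly from assuming equal trends.

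It does not remove the problem. Activity counts are not merely missing from one list; they are placed in the other, which carries an explicit and unsuitable comparison. Intent shown elsewhere supplies no contrast, model or handling of four weeks. If the item instead meant counts during training sessions, daily arm activity would have no stated comparison at all.

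**Conclusion.** The concern holds. As written, section 7 does not test the Aim 2B arm-activity hypothesis: none of the two control-phase wear weeks enters, and one of the three stated occasions has no wear week. This follows from the text and needs no assumption.

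The size of the resulting error is not known from the documents. The 10%, 25% and 72% are illustrations that assume 15 children, independent weekly errors, no RNT effect and an equal trend in each phase. The between-phase contrast keeps 5% only if the trend really is equal in both phases; a shift confined to the control phase raises it to 7%, 15% or 44%.

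The outcome is secondary, data collection is sound and no primary analysis is affected. The plan should be corrected, but this does not threaten the trial as a whole.

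**What to change.** Remove activity counts from the training-specific list and give them their own line, since the three-visit list does not fit four wear weeks either. Specify:

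- a repeated-measures model within child with phase, week in phase and their interaction, using all four wear weeks;
- as the main contrast, matching Aim 2B, (last minus first intervention week) minus (last minus first control week);
- as a sensitivity analysis, because the first intervention week is already treated, the change from last control to last intervention week against the control-phase change;
- all four weekly means, so that a shift confined to one phase, for example at first wear, can be seen.

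Date and document the change. The progress report says analysis of collected data has begun, without saying which data.

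The cost is a few lines in section 7 and in the analysis program; no new data are needed. The downsides are:

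- **Precision.** The detectable difference rises from 1.10 s to 1.56 s.
- **Early effects.** Any effect present in the first intervention week is subtracted from the main contrast, with the loss of power shown above.
- **Sensitivity contrast.** It is less precise. With wear in weeks 1, 6, 7 and 12 it spans six weeks against five, so an equal linear trend of d per phase leaves 0.2d in it. Its rejection rate is then 5.1%, 5.3% or 6.0% for d of 0.25, 0.5 or 1.0 s.
- **Unequal trends.** Neither contrast protects against a trend confined to one phase.
- **Timing.** A contrast fixed after analysis has begun can look data-driven unless it is dated.

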All investigators will provide inputs during protocol development and implementation phases relevant to their specific areas of expertise and project roles. The PI and Co-Is will meet once every week (virtually or inperson) in the initial stages of the study (first 4 months). All procedures related to the study including IRB approval, recruitment, screening and consent procedures, testing and training procedures, toy modifications, etc. will be discussed and finalized during these meetings. The training protocol will thereafter be manualized and shared with all research staff delivering the training with children in their homes/schools/community environments. Once data collection begins, the PI and Co-Is will meet once every month (virtually or in-person) to review ongoing study procedures, timelines, analyses, and study dissemination plans. The PI will meet regularly on a weekly basis with the research staff and will seek Co-I input as needed based on their areas of expertise. The PI will be responsible for training graduate and undergraduate students, checking fidelity of administered measures, ensuring that study procedures adhere to manualized testing and training protocols, developing behavioral coding schemes, and data coding. The PI along with Co-Is will also be responsible for overseeing device modifications, device safety, as well as collection and analysis of kinematic data, and data coming from sensors mounted on the ride-on-toys.

Recruitment Sites

We have identified area hospitals, clinical services, clinicians, and parent advocacy groups in Connecticut and nearby states that we will communicate with for help with recruiting families for the study. Undergraduate and graduate students and the PI will interact with these partners to recruit participants for this study.

RELEVANCE TO AACPDM

The proposed work is in line with the overarching goals within AACPDM's strategic plan pertaining to research, learning innovation, talent pool, partnership and collaboration, as well as service delivery and quality improvement. Improving affected UE spontaneous use and function is one of the most challenging rehabilitation goals for children with hemiplegic CP. We propose a novel therapeutic application of ride-on-toys as an adjunct to conventional UE rehabilitation in CP; our premise is that ride-on-toy navigation practice can incentivize affected UE use in children with hemiplegic CP for the following reasons: (a) ride-on-toys are easy-to-use for clinicians and caregivers alike and can be effectively integrated into the child's play at home, (b) mobility-based games are child-preferred and can promote self-initiated practice using the affected UE for navigation through the physical environment. If our hypotheses are upheld, this innovative project can generate new evidence that has clinical practice implications for management of young children with CP. The project leverages interdisciplinary partnerships across the fields of healthcare and biomedical engineering to develop assistive tools to aid rehabilitation efforts. Based on findings from the proposed project, we will develop future studies that will assess the use of ride-on-toys as therapeutic adjuncts in a variety of settings including school and out-patient settings and administered by a variety of service providers including clinicians,

Check ONE of the following:	
g On Going	
Data Analysis	analyzed, and/or maintained for purposes of publication (i.e., a manuscript has been
submitted but the publisher may ask for revisions that would	
Completed	
A study is considered to be "Completed" if data analysis is do this data for other research purposes requires submission of a	ne, and there is no additional research beyond the original intent planned for this data. Use of a new protocol application.
* Are participants still being enrolled in the stud	dy? ⊠Yes□No
* Have all enrolled participants completed all st	tudy interventions? □Yes ☑No
* Is the research active only for long-term follo	w-up of enrolled participants? □ Yes No
Changes to UConn Key Personnel or Non-U	IConn Investigators:
* Since the last IDP approval (continuing or init	tial) have there have any changes in the personnel working on
the study?	tial), have there been any changes in the personnel working on
If so, create a separate amendment submission indicate whether the personnel are being addeed	n. Submit an IRB-3 Amendment Form with Appendix A - Personnel (to d or removed).
* Has the funding source changed?	
* Has the funding source ended? \Box Yes \blacksquare No	
SECTION IV: Study Summary and Progress Report	
* Findings Describe the current status of the research (e.c	a., phase 1 completed, phase 2 scheduled to start in two months);
provide a summary of findings/analysis conduct	ted during the approval period, state whether the findings are consistent
	escription of the plans for the study during the upcoming approval period.
	ble to simply copy last year's findings section. The IRB must review the eriod. If no work was conducted on this study during the last approval
period, please state so and explain why (e.g., t	oo busy with other projects, delay in funding, unable to hire a graduate
student to work on the project, etc.). If closing resulting from the study.	the study, please attach a copy of any publications or manuscripts
	e joystick-operated ride-on-toy navigation intervention within community
settings in children with cerebral palsy. We have	e completed data collection with 12 children with cerebral palsy (11
	y completed study procedures). Presently, 4 children are at various hildren are in the intervention phase, 2 children are in the control phase
of the study). Our plan is to complete data colle	ection with these 4 children by the end of the Spring semester. We will
	ar into 2025. So far, our observations suggest that data collection is
proceeding smoothly with no adverse events. V	Ve have also simultaneously begun analyzing data collected from children

JConn IRB Protoco	I H22-0059	Annroved	March 7	2024

Important: If more p 5), and submit with th Additionally, if you wis 3), and submit with th eport of Participants Screened Identify each Participant Population in this column (e.g. Children, Adults)	his Re-approval/Termina ish to increase the total his Re-approval/Termina (if applicable) Since last IRB revi participants who	anticipated enrollment, p ation form.		Iment Review Form (IRB-
Important: If more p 5), and submit with th Additionally, if you wis 3), and submit with th eport of Participants Screened Identify each Participant Population in this column (e.g. Children, Adults)	participants were enrolle his Re-approval/Termina ish to increase the total his Re-approval/Termina (if applicable) Since last IRB revi participants who Failed screen and we removed by PI	ation form. anticipated enrollment, p ation form. wew, report total # of ere Passed screen and were enrolled into study	lease complete an Amend Total # of participan who Failed screen and were removed by PI	Iment Review Form (IRB- ts screened to date Passed screen and were enrolled into study
Important: If more p 6), and submit with th Additionally, if you wis 3), and submit with th	participants were enrolle his Re-approval/Termina ish to increase the total his Re-approval/Termina (if applicable) Since last IRB revi participants who Failed screen and we removed by PI	ation form. anticipated enrollment, p ation form. wew, report total # of ere Passed screen and were enrolled into study	lease complete an Amend Total # of participan who Failed screen and were removed by PI	Iment Review Form (IRB- ts screened to date Passed screen and were enrolled into study
Important: If more p 5), and submit with th Additionally, if you wis 3), and submit with th eport of Participants Screened Identify each Participant Population in this column (e.g.	participants were enrolle his Re-approval/Termina ish to increase the total his Re-approval/Termina (if applicable) Since last IRB revi participants who Failed screen and we	ation form. anticipated enrollment, p ation form. wew, report total # of ere Passed screen and were enrolled into	lease complete an Amend Total # of participan who Failed screen and were	Iment Review Form (IRB- ts screened to date
Important: If more p 6), and submit with th Additionally, if you wis 3), and submit with th eport of Participants Screened Identify each Participant Population in this column (e.g.	participants were enrolle his Re-approval/Termina ish to increase the total his Re-approval/Termina (if applicable) Since last IRB revi	ation form. anticipated enrollment, p ation form. www.report total # of	lease complete an Amend	Iment Review Form (IRB-
Important: If more p 6), and submit with th Additionally, if you wis	participants were enrolle his Re-approval/Termina sh to increase the total his Re-approval/Termina	ation form. anticipated enrollment, p ation form.		
Important: If more p 6), and submit with th Additionally, if you wis	participants were enrolle his Re-approval/Termina sh to increase the total	ation form. anticipated enrollment, p		
		′es □ No		
Total	1	16	17	
Paisy				
Children with Cerebral palsy	1	since last IRB review.	17	0
Participant Population in this column (if more tha one, identify each)	last approval perio an (TOTAL # from las	reading an information sheet)	years plus this year) See "Important"	
Identify each	# of participants	# of participants	Total # of	
ECTION VI: Participants For each participant p	population, please comp	lete the following:		
•	eing amended per this si view Form (IRB-3) ne			
ECTION V: Amendments				
believe that no such l		e "No literature exists"		
		y other authors that provi ch articles to this form. If		
		ost recent DSMB report.	nitoring plans/board mee	tings and the date of the
		age of the data cafety me		
or "No." If applicable, provide	a summary of the findir	ct a participant's willingne	ss to continue this study?	Indicate "Yes" □Yes ☑No

								- k	
	s available , d for NIH fu		number of part Irch.	icipants enro	olled to dat	e in each of th	e categories	s below. This	information
	American Indian/ Alaska Native	Asian	Black or African American	Hispanic or Latino	White	Native Hawaiian or Other Pacific Islander		Unknown or Not Reported	
emale	2		1	5		-	1		9
lale	1		2	4		1			8
rans-	`		-	·		-			
nknown otal		3	1	2	9			2	
	: Events to be R		-Approval rotocol deviati	ons reported	to the IRB	during the las	+ approval r	period? Dvar	
	106136 60611								
CTION VII:	: Events to be R	leported at Re	-Approval						
			and Protocol						
	g to the IR for further		dance with t on.	ne Adverse	Event/Pro	otocol Deviat	ion policy.	Please see	the IRB
